**SYNOPSIS**

Protocol ID	NAXIVA
Protocol Title	Phase II Neoadjuvant study of AXItinib for reducing extent of venous tumour thrombus in clear cell renal cell cancer with Venous invAsion (NAXIVA)
Development Phase	Phase II Feasibility
Primary Endpoint	
The percentage of evaluable patients with an improvement in the Mayo classification.
 
Mayo Classification:
 
 
• Level 0: thrombus limited to the renal vein
 
• Level 1: into IVC <2cm from renal vein ostium level
 
• Level 2: IVC extension >2cm from renal vein ostium and below hepatic vein
 
• Level 3: thrombus at the level of or above the hepatic veins but below the diaphragm
 
• Level 4: thrombus extending above the diaphragm.
 

Secondary Endpoints	
% change in surgical approach.
 
% change in venous tumour thrombus (VTT) height.
 
Response rate (RECIST).
 
Evaluation of morbidity assessed by Clavian-Dindo classification.

Study Design	NAXIVA is a single arm, single agent, open label, phase 2 feasibility study of axitinib in patients with both metastatic and non-metastatic renal cell carcinoma of clear cell histology prior to nephrectomy and thrombectomy.
Patient Accrual	20 patients will be recruited over a 24 month period at 7 sites across the UK.
Interim Analysis	Will be performed after thirteen patients have been recruited. If no patients show an improvement in their Mayo classification the trial will be stopped for futility.

**GLOSSARY OF ABBREVIATIONS**

AE	Adverse Event
AIDS	Acquired Immunodeficiency Syndrome
ALT	Alanine Transaminase
AR	Adverse Reaction
AST	Aspartate Transaminase
BID	Twice a day
BP	Blood Pressure
ccRCC	Clear Cell Renal Cell Cancer
CI	Chief Investigator
CRF	Case Report Form
CRP	C-Reactive Protein
CRUK	Cancer Research United Kingdom
CSA	Common Services Agency
CT	Computed Tomography
CTCAE	Common Toxicity Criteria for Adverse Events
ct DNA	Circulating Tumour DNA
DCE	Dynamic Contrast Enhanced
DMC	Data Monitoring Committee
DWI	Diffusion Coefficient
EDTA	Ethlenediaminetetraacetic Acid
EMT	Epithelial Mesenchymal Transition
EU	European Union
GCP	Good Clinical Practice
GP	General Practitioner
HIV	Human Immunodeficiency Virus
ICH	International Conference on Harmonisation
IC50	50% Inhibitory Concentration
IMP	Investigational Medicinal Product
IVC	Inferior Vena Cava
LDH	Lactate Dehydrogenase
M0	Non-metastatic
M1	Metastatic
MHRA	Medicines and Healthcare products Regulatory Agency
mRCC	Metastatic Renal Cell Carcinoma
MRI	Magnetic Resonance Imaging
MSKCC	Memorial Sloan Kettering Cancer Centre
NSCLC	Non Small Cell Lung Cancer
ORR	Objective Response Rate
PBS	Phosphate Buffered Saline
PCR	Protein: Creatinine Ratio
PDGF-R	Platelet-Derived Growth Factor Receptors
PI	Principal Investigator
PIL	Patient Information Leaflet
PMBC	Peripheral Blood Mononuclear Cells
PRES	Posterior Reversible Encephalopathy Syndrome
PSA	Prostate-specific antigen
QP	Qualified Person
RCC	Renal Cell Cancer
R&D	Research and Development
REC	Research Ethics Committee
RECIST	Response Evaluation Criteria in Solid Tumours
SAE	Serious Adverse Event
SCTRU	Scottish Clinical Trials Research Unit

SDV	Source Data Verification
SmPC	Summary of Product Characteristics
SOP	Standard Operating Procedures
SUSAR	Suspected Unexpected Serious Adverse Reaction
TKI	Tyrosine Kinase Inhibitor
TMG	Trial Management Group
TSC	Trial Steering Committee
TSH	Thyroid Stimulating Hormone
TTP	Thrombotic Thrombocytopenic Purpura
TV	Tumour Thrombus Volume
UKCRC	United Kingdom Clinical Research Collaboration
ULN	Upper Limits of Normal
VEGF	Vascular Endothelial Growth Factor
VEGFR	Vascular Endothelial Growth Factor Receptor
VTT	Venous Tumour Thrombus

## 1. INTRODUCTION

### 1.1. Background

Venous tumour thrombus (VTT) extension into the renal vein and/or inferior vena cava (IVC) occurs in 4-15% cases of renal cell cancer (RCC) (1). If the patient is fit enough to undergo surgery, in an attempt to excise all disease with curative intent, the surgical risk is high due to the need to perform a cavotomy and/or open heart surgery to excise the VTT (5-15% mortality) (1). Complications are established to increase with the height of the VTT (1). After such surgery, the 5 year survival rates are poor; ~40-65% in non-metastatic RCC to 0-17% for patients with concomitant metastatic RCC (2, 3). As such, the concept of using targeted therapies, which are standard of care in metastatic RCC, to downstage the VTT prior to extirpative surgery is appealing. If it were possible to reduce the extent of the surgery an individual patient with RCC VTT required it is likely morbidity and mortality would be reduced and potentially survival time improved.

### 1.2. Investigational Medicinal Product

Axitinib is a potent oral VEGFR2 and 3 inhibitor at picomolar concentrations and VEGFR1, PDGFRs and c-KIT inhibitor at low nanomolar concentrations. In phase II clinical trials, axitinib has shown efficacy in sorafenib and cytokine refractory mRCC patients. A recently reported phase III trial, showed superiority over sorafenib as second line therapy (4), leading to the licensing of axitinib in this indication by the United States Food and Drug Administration (FDA) agency in January 2012. Axitinib was subsequently licensed for the same indication by the European Medicines Agency. Furthermore, the efficacy of axitinib is under evaluation in other tumour types, and has shown activity in lung (5), thyroid (6), and pancreatic (7) cancers, and melanoma (8).

### 1.3. Pre-Clinical Data

In vitro, axitinib inhibits cellular phosphorylation of VEGFR2 and 3 with an IC50 of about 0.2 nmol/L. It has a higher IC50 for VEGFR1 (1.2 nmol/L), PDGFR- $\beta$  (1.6 nmol/L), PDGFR- $\alpha$  (5 nmol/L) and c-KIT (1.7 nmol/L). It reduces phosphorylation of downstream signalling molecules mediated by vascular endothelial growth factor (VEGF) in a rapid and dose-dependent manner, including Akt, endothelial nitric oxide synthase and extracellular signal regulated kinase (ERK).

In mouse xenografts, twice daily oral axitinib inhibited the primary tumour and controlled metastases in human melanoma (M24mwt), colorectal cancer (HCT-116) and RCC (SN12C) models. Within axitinib treated tumours, there was reduced CD31 and Ki-67 staining and increased caspase-3 staining. Microscopic examination of tumour vasculature in preclinical models of pancreatic islet cell tumours and Lewis lung carcinomas has shown that axitinib reduces patency and flow. Axitinib has its greatest effects on endothelial cells and fenestrated vessels, resulting in normalisation of the surviving tumour vasculature.

### 1.4. Clinical Data

#### 1.4.1 Efficacy Data

##### Phase I

In an initial phase I study, 3 of 36 patients had partial responses determined by Response Evaluation Criteria in Solid Tumours (RECIST) (9) including 2 patients with RCC and 1 patient with adenoid cystic carcinoma (10). In a Japanese phase I trial, none of 12 recruited patients had a partial response but 3 patients had stable disease at 24 weeks, seen in one patient each with colorectal carcinoma, thymic cancer and non-small cell lung cancer (NSCLC) (11).

**Phase II: Axitinib in Cytokine-refractory Metastatic RCC**

In a single arm, open label, phase II trial in cytokine-refractory mRCC, axitinib was administered at a starting dose of 5mg twice daily in the fasted state as 28 day treatment cycles until disease progression or significant toxicity (12). Fifty-two patients were recruited with a median age of 59 years and performance status 0 or 1. Forty-nine patients (95%) had previously undergone a nephrectomy and none of the patients had previously received tyrosine kinase inhibitors (TKIs). All patients had clear cell histology, except one patient who had papillary carcinoma. The objective response rate (ORR) was 44.2% (95% CI: 30.5-58.7%); there were 2 complete and 21 partial responses. Twenty-two patients had stable disease for at least 8 weeks, including the patient with papillary carcinoma. Four patients had early progression and 3 patients could not be assessed for response. The median thrombotic thrombocytopenic purpura (TTP) was 15.7 months and median overall survival was 29.9 months. The median duration of axitinib therapy was 9.4 months and median dose was 8.83 mg/day, as 15 patients had dose reductions for adverse events (AE) including fatigue, hypertension and diarrhoea. Axitinib was discontinued due to adverse events in ten patients. The most frequent grade 1-4 axitinib related adverse events were diarrhoea, hypertension, fatigue, nausea and hoarseness. The most common grade 3-4 adverse events were hypertension (15.4%), diarrhoea (9.6%) and fatigue (7.7%). Thirty patients had axitinib induced hypertension, eight of whom had grade 3-4 hypertension. Hypertension was resistant to anti-hypertensive therapy in 8 patients, seven of whom had hypertension at baseline. There were no detectable haematological toxicities. Four patients had treatment related proteinuria which resolved once axitinib was stopped.

**Phase II: Axitinib in Sorafenib Refractory Metastatic RCC**

In a single arm, open label, phase II study, patients with sorafenib refractory mRCC received a starting dose of axitinib 5mg twice daily with food until disease progression or unmanageable toxicity (13). Sixty-two patients were recruited; all had undergone prior nephrectomy and 59 patients had clear cell /mixed histology. Median age was 60 years and all patients were performance score of 0 or 1. The most common prior therapies in addition to sorafenib were sunitinib and cytokine therapy, received by 14 (22.6%) and 38 (61.3%) patients, respectively.

The ORR was 22.6% (95% CI 12.9-35.0%), with 14 patients experiencing a partial response and no complete responses. Tumour responses were observed in patients who received 5 mg twice daily or higher, and also in patients whose dose was reduced to below 5 mg twice daily. Patients who had a partial response received doses ranging from <4mg to 9-10mg twice daily. Eleven patients (17.8%) had stable disease. The median progression-free survival was 7.4 months (95% CI 6.7-11.0 months) and median overall survival was 13.6 months (95% CI 8.4-18.8 months).

The most common grade 3-4 adverse events included hypertension (16.1%), fatigue (16.1%), hand-foot syndrome (16.1%), dyspnoea (14.5%) and diarrhoea (14.5%). Twelve patients stopped axitinib due to treatment related adverse events. Two patients developed congestive heart failure, both of whom had a history of cardiovascular disease, and two patients had cerebral haemorrhages during the study. One of the latter patients was subsequently diagnosed with a cerebral metastasis at the site of haemorrhage. Most haematological toxicities were mild or moderate (grade 1 or 2) except grade 3 lymphopaenia experienced by 9 of 55 evaluable patients (16.4%).

**1.4.2 Safety Data****Phase I**

The primary dose limiting toxicity in the initial phase I trial was hypertension (10); in most cases it responded to anti-hypertensive therapy and resolved after axitinib was stopped. The incidence and severity of hypertension was dose-dependent, all patients with axitinib-

induced hypertension at dose 5mg twice daily were managed with standard anti-hypertensives. Prior to blood pressure monitoring two patients had uncomplicated seizures in the absence of brain metastases at doses 10mg and 20mg twice daily, these may have been related to hypertensive crises.

Three bleeding events were reported during the phase I study. A patient with central NSCLC had a fatal haemoptysis attributed to axitinib. A patient with peripheral NSCLC had grade 1 haemoptysis while taking axitinib which was subsequently stopped. Two weeks later the patient had grade 4 haemoptysis and died, this patient's death was reported as secondary to disease progression and concurrent infection. Finally, there was 1 episode of grade 1 rectal bleeding.

Asymptomatic proteinuria was detected in seven of the first ten patients. Consequently, patients with proteinuria  $>0.5\text{gram}/24\text{ hours}$  were not recruited and treatment reviews were required for all patients with proteinuria  $\geq 1\text{gram}/24\text{ hours}$ . These amendments reduced the incidence and severity of proteinuria.

Thrombocytopenia was the only haematological toxicity in the phase I trial, with grade 2 thrombocytopenia affecting one patient taking 20mg twice daily.

## Phase II

The commonest non-haematological adverse events grade 1-4 reported in phase II axitinib monotherapy trials were hypertension, fatigue, diarrhoea, anorexia, nausea and hoarseness. The main grade 3-4 adverse events were similar, except hand-foot syndrome and proteinuria were also reported. Most adverse events were manageable. Hypertension usually responded to anti-hypertensive therapy and resolved once axitinib was stopped.

The starting dose in all but one of the phase 2 studies conducted to date was 5mg twice daily of axitinib. In one metastatic breast cancer study, axitinib dose was titrated up from a starting dose of 5mg twice daily in 1–3mg increments in patients tolerating axitinib. Those subjects who could tolerate axitinib with no adverse events related to axitinib above CTCAE (14) grade 2 for consecutive 2 week periods were permitted to increase their dose step-wise to 7mg twice daily and then to 10mg twice daily, unless their BP was  $>150/90\text{mm Hg}$  or the subject was receiving antihypertensive medication. All studies ongoing at the time of writing allow axitinib dose reductions to as low as 2mg twice daily for treatment-related adverse events. Except for an increase in hand-foot syndrome and slight increase in the incidence of hypertension, it appears that patients whose dose is titrated to between 6-10mg twice daily doses do not experience increased toxicities if they have previously tolerated 5mg twice daily starting dose. Axitinib dose titration will be permitted within NAXIVA, consistent with previous clinical trial protocols and the drug development programme for axitinib.

### 1.5. Trial Rationale

There is no level I or II evidence of neoadjuvant studies of targeted therapies in non-metastatic RCC VTT or upfront therapies in metastatic RCC VTT. There is level III evidence of mixed populations of RCC VTT patients (including both metastatic and non-metastatic patients) treated with a heterogeneous group of drug treatments (15, 16). The results of these studies suggest that regression in VTT is limited to sunitinib therapy (seen in 3/12=25% patients; regression not seen for bevacizumab, temsirolimus or sorafenib). With sunitinib treatment none of the patients (0/12) had an increase in the VTT level (15).

A recent prospective phase II of 12 weeks neoadjuvant axitinib in ccRCC T2-T3b, has been reported by Karam and colleagues (17). All of the patients in this study were cT3a (i.e. there were no patients with VTT). It was possible to titrate all patients up to 10mg axitinib with no grade 4/5 toxicities. 100% of patient's tumours showed response (46% patients had partial response, and 54% stable disease) and the median reduction in primary tumour diameter was 28% by week 12. The median tumour diameter reduced from 10cm to 6.9cm. The vast majority of reduction in tumour size had occurred at 7 weeks of axitinib treatment.

The results of these small studies in non-metastatic RCC patients suggest that neoadjuvant TKI treatment of RCC patients is safe. However, the effect of these drugs on the extent of the VTT and the surgical approach that must be applied has not been confirmed. Authors in this field agree that a prospective trial is required to answer this important clinical question (15,16,18).

In NAXIVA we will study the response of VTT to axitinib. The primary outcome is percentage of patients with reduction in the Mayo Classification (19). This study will address the feasibility of patient recruitment in this setting. In order to ensure adequate recruitment both metastatic and non-metastatic patients will be recruited to assess the effect of axitinib therapy on the extent of the tumour thrombus, rather than to primarily assess a prolonged survival. A reduction in the extent of the VTT, as assessed by the Mayo classification, will potentially result in less extensive and less morbid surgical approach with immediate patient benefits of reduced operative mortality/morbidity, potential shorter hospital stay and shorter recuperation period to return to full activities of daily living. There is also potential for a longer disease free survival in patients treated with axitinib prior to nephrectomy and tumour thrombectomy. The risks of the treatment of patients with VTT with axitinib over an 8 week period include progression of their disease (from operable to non-operable or non-metastatic to metastatic). However, based on the studies outlined above there is no evidence that progressive disease will occur over this period of time. Treating patients with axitinib over an 8 week period may also increase the incidence of adverse events which could have a significant impact on the patient's fitness for surgery. This risk will be minimised as dose reduction and axitinib cessation will be managed as per section 4.

Axitinib has been chosen for this study as it is a potent TKI with proven effect in non-metastatic ccRCC (17). The dose regimen (starting at 5mg bd, increasing dose up to 10mg twice daily (BID), as rapidly as possible, as tolerated by patients) is a well established regimen in metastatic ccRCC and was shown to be effective in the previous non-metastatic ccRCC neoadjuvant study (18). 8 weeks has been chosen as the treatment duration as in the study by Karam et al maximum effect on the primary tumour size was observed by 7 weeks and no significant further advantage was seen by continuing treatment to 12 weeks.

Patients having biopsy proven ccRCC will be included in this study, as this is histological subtype of RCC shown to have a benefit from axitinib therapy. Patients with VTT confined to the renal vein (cT3a) will be included as they would benefit from a reduction in the extent of the VTT, regressing from the renal vein back into the kidney, as this would allow curative surgery by laparoscopic rather than more morbid open surgical approaches. Patients with more extensive IVC VTT (infrahepatic, intrahepatic or atrial) will be included, as for patients in each of these groups reducing the extent of the thrombus i.e. from intrahepatic to infrahepatic would potentially reduce extent of surgery and the associated surgical morbidity. Both non-metastatic and metastatic patients will be eligible for recruitment as both groups of patients are likely to benefit, in terms of reduction of level of VTT and surgical morbidity, if axitinib shows efficacy in this patient cohort. It is accepted that there may be different biological processes at play in these 2 cohorts. However, this will be further explored in a fully powered phase 3 randomised control trial, if this phase 2 trial is positive.

## 2. TRIAL OBJECTIVES

**Aims:** to assess the reduction in the Mayo Venous Tumour Thrombus Classification of patients with clear cell renal cell cancer who have a renal vein or inferior vena cava venous tumour thrombus treated with neoadjuvant (non-metastatic patients) or upfront (metastatic patients) axitinib therapy.

**Primary outcomes:**

- The percentage of evaluable patients with an improvement in the Mayo Classification.

**Mayo Classification:**

- Level 0: thrombus limited to the renal vein
- Level 1: into IVC <2cm from renal vein ostium level
- Level 2: IVC extension >2cm from renal vein ostium and below hepatic vein
- Level 3: thrombus at the level of or above the hepatic veins but below the diaphragm
- Level 4: thrombus extending above the diaphragm.

**Secondary outcomes:**

- % change in surgical approach
- % change in VTT height
- Response rate (RECIST)
- Evaluation of surgical morbidity assessed by Clavien-Dindo classification

## 3. TRIAL DESIGN

### 3.1. General Design

NAXIVA is a single arm, single agent, open label, phase II feasibility study of axitinib in patients with both metastatic and non-metastatic renal cell carcinoma of clear cell histology. 20 patients will be recruited from multiple centres within the United Kingdom.

Patients who have signed informed consent and who have met all eligibility criteria will be registered into the trial.

The starting dose of axitinib will be 5mg BID and escalated to 7mg BID and then 10mg BID. A dose modification assessment will take place every 2 weeks in clinic during the 8 week pre-surgical treatment period and will be dependent on tolerability of treatment. Patients will follow an aggressive axitinib dose escalation process within the 8 week period to a maximum of 10mg BID. Patients should stop axitinib a minimum of 36 hours and a maximum of 7 days prior to surgery in week 9.

Blood, urine and tissue samples will be taken prior to and during therapy to evaluate biomarkers of treatment response. Nephrectomy and IVC tumour thrombectomy will be planned for all patients on the trial.

Response to axitinib in VTT, primary tumour and any RECIST measureable lesion will be correlated with changes in molecular markers.

Patients will be followed up in clinic at 6 & 12 weeks post surgery.

### 3.2. Inclusion Criteria

1. Age  $\geq$  18.
2. Histologically proven clear cell RCC.
3. Immediate resection of the primary tumour considered technically possible.

4. Suitable for and willing to undergo nephrectomy (either cytoreductive or with curative intent)
5. cT3b, cT3c, cT3a (main renal vein)
6. N0, N1, or Nx
7. M0, or M1
8. ECOG performance status 0 – 1
9. Urinalysis  $<2+$  protein. If dipstick is  $\geq 2+$  then a 24-hour urine collection should be performed and the patient may enter NAXIVA only if urinary protein is  $<2$ g per 24 hours.
10. All female patients with reproductive potential must have a negative serum or urine pregnancy test within a maximum of 14 days prior to starting trial treatment.

### **3.3. Exclusion Criteria**

1. For M1 patients: poor risk on Memorial Sloan Kettering Cancer Centre (MSKCC) score and deemed suitable for cytoreductive nephrectomy at time of enrolment.
2. The presence of active second malignancy. Patients will be eligible if they have adequately treated basal cell carcinoma, squamous cell skin cancer, in situ cervical cancer, stable prostate cancer or if treated with curative intent for any other cancer with no evidence of disease for 2 years. Patients with prostate cancer will be permitted entry if not receiving treatment and prostate-specific antigen (PSA) is not rising.
3. Women who are pregnant or are breastfeeding. Female patients must be surgically sterile, be postmenopausal, or must agree to use effective contraception during the period of therapy and up to 1 week after treatment.  
Male patients must be surgically sterile or must agree to use effective contraception during the period of therapy and for 6 months after completion of study drug (Patients who do not meet this will not be are not eligible).
4. Current signs or symptoms of severe progressive or uncontrolled hepatic, endocrine or pulmonary disease other than directly related to RCC.
5. Gastrointestinal abnormalities including: a. inability to take oral medication; b. requirement for intravenous alimentation; c. prior surgical procedures affecting absorption including total gastric resection; d. treatment for active peptic ulcer disease in the past 6 months; e. active gastrointestinal bleeding, unrelated to cancer, as evidenced by hematemesis, hematochezia or melena in the past 3 months without evidence of resolution documented by endoscopy or colonoscopy; f. malabsorption syndromes.
6. Current use or anticipated need for treatment with drugs that are known potent CYP3A4 inhibitors (see section 4.4, concomitant therapy).
7. Current use, or anticipated need for treatment with, drugs that are known CYP3A4 inducers or substrates for CYP1A2 (see section 4.4, concomitant therapy).
8. Requirement of anticoagulant therapy with oral vitamin K antagonists. Low-dose anticoagulants for maintenance of patency of central venous access device or prevention of deep venous thrombosis is allowed. Therapeutic use of low molecular weight heparin is allowed.
9. Active seizure disorder, spinal cord compression, or carcinomatous meningitis.
10. Any of the following within 12 months prior to study entry: myocardial infarction, uncontrolled angina, coronary/peripheral artery bypass graft, symptomatic congestive heart failure, cerebrovascular accident or transient ischemic attack.
11. Uncontrolled hypertension ( $>160/100$  mmHg despite optimised antihypertensive treatment).
12. Known human immunodeficiency virus (HIV) or acquired immunodeficiency syndrome (AIDS)-related illness.
13. ALT or AST  $\geq 1.5 \times$  ULN; Bilirubin  $\geq 1.5 \times$  ULN.
14. Serum creatinine  $\geq 1.5 \times$  ULN

15. Neutrophil count  $< 1.0 \times 10^9/L$ ; platelet count  $< 100 \times 10^9/L$ ; Hb  $\leq 90g/L$ .
16. Known severe hepatic impairment (Child-Pugh class C)
17. Known hypersensitivity to axitinib or any of its excipients. Specifically patients with hereditary galactose intolerance, Lapp lactase deficiency or glucose-galactose malabsorption should not enter the study.

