#### **4.4. Concomitant Therapy**

Axitinib is metabolised primarily by liver enzymes, in particular CYP3A4. All medication considered necessary for the patients' welfare and which is not expected to interfere with the evaluation of the study drug may be given at the discretion of the investigator. Concomitant medications must be recorded in the patients' source documentation, as well as the appropriate pages of the CRF.

Contraindicated concurrent medications include:

Agents known to induce CYP3A4 or CYP1A2 including but not limited to:	Agents known to inhibit CYP1A2, CYP2C19 or CYP3A4 including but not limited to:

 
○ Amobarbital,
 
○ Carbamazepine,
 
○ Dexamethasone,
 
○ Felbamate,
 
○ Nevirapine,
 
○ Omeprazole,
 
○ Phenobarbital,
 
○ Phenytoin,
 
○ Primidone,
 
○ Rifabutin,
 
○ Rifampicin,
 
○ St John's wort
 
	
 
○ Amitriptyline
 
○ Amprenavir,
 
○ Artemisinin,
 
○ Atazanavir,
 
○ Atazanavir,
 
○ Cimetidine,
 
○ Ciprofloxacin,
 
○ Clarithromycin,
 
○ Delavirdine
 
○ Enoxacin,
 
○ Erythromycin,
 
○ Ethinyl,
 
○ Fluvoxamine,
 
○ Fosamprenavir
 
○ Grapefruit juice,
 
○ Imipramine
 
○ Indinavir,
 

	
 
 Itraconazole,
 
 Ketoconazole,
 
 Lopinavir,
 
 Mexiletine,
 
 Miconazole,
 
 Nelfinavir,
 
 Ritonavir,
 
 Saquinavir,
 
 Tacrine,
 
 Telithromycin,
 
 Thiabendazole,
 
 Ticlopidine.
 
 Verapamil,
 
 Zileuton
 

--	--

- Other approved or investigational systemic anticancer treatments, including chemotherapy, hormone therapy and immunotherapy.
- Other investigational drugs.

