The use of potent antacids such as proton pump inhibitors (except those listed above) and histamine H2 antagonists is permissible, if medically necessary. However, patients requiring chronic antacid therapy should avoid their use for 2 hours before and for 2 hours after taking axitinib tablets.

The contraindicated medications detailed above may only be used in exceptional circumstances and following written confirmation from SCTR U of the CI's approval.

The current version of the SmPC should be used to assess whether any other concomitant medications are permissible.

Other supportive medicines such as thyroid replacement therapy, anti-emetics and anti-diarrhoeal medicines are permitted in accordance with local practice.

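### Section 4.4 contraindicates cimetidine by name, yet its antacid paragraph permits H2 antagonists without excepting it; secondarily, exclusion 7 cites 4.4 for CYP1A2 substrates, a class 4.4 does not name

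*Protocol*

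**What the plan says.** Protocol section 4.4 sets out contraindicated drugs in two columns. The first is headed "Agents known to induce CYP3A4 or CYP1A2 including but not limited to" and includes omeprazole. The second is headed "Agents known to inhibit CYP1A2, CYP2C19 or CYP3A4 including but not limited to" and includes cimetidine.

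Three further provisions of 4.4 follow the table:

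- On acid suppression: "The use of potent antacids such as proton pump inhibitors (except those listed above) and histamine" H2 "antagonists is permissible, if medically necessary". Patients on chronic antacids must also keep them two hours apart from axitinib.
- On the listed drugs: "The contraindicated medications detailed above may only be used in exceptional circumstances and following written confirmation" of the Chief Investigator's approval, given through the trials unit.
- On anything else: "The current version of the SmPC should be used to assess whether any other concomitant medications are permissible".

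The section opens with a general rule: medication needed for the patient's welfare "which is not expected to interfere with the evaluation of the study drug may be given at the discretion of the investigator".

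At entry, exclusion 7 in section 3.3 bars "Current use, or anticipated need for treatment with, drugs that are known CYP3A4 inducers or substrates for CYP1A2 (see section 4.4, concomitant therapy". Exclusion 6 bars potent CYP3A4 inhibitors and also points to 4.4.

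**The concern.** Cimetidine is an H2 antagonist. Section 4.4 therefore attaches two different conditions to it. As a named inhibitor it needs exceptional circumstances and written approval. As an H2 antagonist it needs only medical necessity and the two-hour spacing. A prescriber or pharmacist who looks up antacids could read the permission, see that the exception is attached to the other class, and dispense cimetidine without contacting the trials unit. Section 4.4 itself says axitinib is cleared mainly by liver enzymes, CYP3A4 in particular, and section 3.1 escalates the dose to as much as 10 mg twice daily. The rules on enzyme inhibitors should therefore leave no doubt.

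The secondary matter is a cross-reference. Exclusion 7 sends the reader to 4.4 for CYP1A2 substrates, and 4.4 has no such class. A site checking eligibility finds nothing there to say which drugs are meant, or whether they may be started once treatment is under way.

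**Working it through.** No alpha, power, rate or sample size enters this point, so there is no figure in the plan to reproduce. The check is a comparison of texts and a count.

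**Step 1. Count the agents named in 4.4.** The inducer column has 12 entries. The inhibitor column has 31, with atazanavir entered twice, so 31 − 1 = 30 distinct. Total: 12 + 30 = 42 distinct agents.

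**Step 2. Find the acid suppressants among them.** There are two: omeprazole (a proton pump inhibitor, inducer column) and cimetidine (an H2 antagonist, inhibitor column). The drug classes are general pharmacology; the protocol does not state them.

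**Step 3. Apply the antacid paragraph to each.**

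| Agent | In the contraindicated table | Class permitted in the antacid paragraph | Exception for listed drugs attached to that class | Result |
|---|---|---|---|---|
| Omeprazole | Yes | Yes | Yes | One rule: approval needed |
| Cimetidine | Yes | Yes | No | Two rules: approval needed, or medical necessity alone |

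The bracket resolves the overlap for one of the two agents and leaves the other. So 1 of the 42 named agents is both contraindicated by name and inside a class permitted without an exception.

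**Step 4. Compare the classes at entry with those in 4.4.**

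| Class | Exclusions 6–7 | Section 4.4 |
|---|---|---|
| CYP3A4 inducers | barred | contraindicated |
| Potent CYP3A4 inhibitors | barred | contraindicated |
| Other CYP3A4 inhibitors | not barred | contraindicated |
| CYP1A2 inducers | not barred | contraindicated |
| CYP1A2 inhibitors | not barred | contraindicated |
| CYP2C19 inhibitors | not barred | contraindicated |
| CYP1A2 substrates | barred | not named |

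Two classes match, four are restricted only on treatment, and one is restricted only at entry: 2 + 4 + 1 = 7. The four are not errors, because a protocol may leave a drug off the entry criteria and control it during treatment. The last row differs in that the entry criterion cites 4.4 for a class that 4.4 does not contain. The open-ended wording of the two column headings does not fill the gap: it extends lists of inducers and inhibitors, and a substrate is neither by virtue of being a substrate.

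**Step 5. Ask what controls a CYP1A2 substrate on treatment.** If the drug falls in no other listed class, the controls are investigator discretion, limited to drugs not expected to interfere with evaluating axitinib, and the SmPC check. The written-approval rule applies to the drugs detailed in 4.4 and does not reach it.

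**The case against.** **On cimetidine.** The strongest reply is that the section can be read as consistent. A drug prohibited by name ordinarily prevails over a general permission for its class, and the sentence restricting contraindicated drugs to exceptional use comes after the antacid paragraph and covers every listed drug. That is probably how a careful reader would resolve it, so a flat charge of self-contradiction would go too far. What remains is that 4.4 spells out this priority for proton pump inhibitors and is silent for H2 antagonists, so the reader has to supply it. A safety rule should not depend on that inference when moving one bracket removes the need.

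**On CYP1A2 substrates.** Here more of the objection stands. A sponsor may properly refuse patients with a foreseeable need for a drug class while leaving unforeseen needs to clinical judgement and the SmPC. A correctly enrolled patient had neither current use nor anticipated need, so a later start is a new situation and not the one barred at entry. The SmPC check is a real control, although what it says about CYP1A2 substrates cannot be seen from these documents.

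**Stronger readings that a reader might infer.** One is that either exclusion 7 or 4.4 must be wrong. Nothing in the protocol requires the two to coincide, so this does not follow. Another is that the word substrates is a slip for inducers, because 4.4's first heading pairs CYP3A4 with CYP1A2 inducers. That is possible, but no text shows it, and removing an entry exclusion on a guess is the wrong way round for a safety criterion. A third is that the wording costs recruitment in a 20-patient trial. Turning patients away is what an exclusion does, and the documents give no basis for counting those affected.

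**Conclusion.** The cimetidine wording should be corrected. As written, one named drug has two conditions in an operative safety rule, and the less strict one omits the required approval. This rests only on the text and on cimetidine being an H2 antagonist.

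The exclusion 7 mismatch is real but secondary. It supports a question to the sponsor, not a finding that either passage is in error.

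This is a minor safety-consistency correction. The number of patients who might be given cimetidine, or who take a CYP1A2 substrate, cannot be estimated from the documents. The primary endpoint, the stopping rules and the Simon two-stage figures do not depend on it.

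**What to change.** 1. In the antacid paragraph of 4.4, move the bracketed exception so that it follows both classes: proton pump inhibitors and histamine H2 antagonists (except those listed above). Cimetidine is then governed only by the approval rule. H2 antagonists that 4.4 does not contraindicate stay permitted.
2. Ask the sponsor which CYP1A2 class exclusion 7 is meant to cover. By default keep the exclusion as it stands and add CYP1A2 substrates to 4.4, so that the cross-reference has a target and the approval rule applies on treatment. Change exclusion 7 to CYP1A2 inducers only if the sponsor confirms that substrates was a slip.

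No further rule on contraindicated drugs before enrolment is needed. The classes that 4.4 restricts and the entry criteria do not are not errors, and a general route to entry by written approval would sit badly with exclusions 6 and 7, which offer none.

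The cost is one moved bracket, one sponsor query and one resulting wording edit, with a matching line on the eligibility checklist if exclusion 7 changes. No visit, test or patient is added. Adding substrates to 4.4 would bring some approval requests that the present text does not require.
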